**Table 5. Dose Modifications of Trigriluzole**

Protocol Number: RCINJ# 051707

PI Name: [name]

Protocol Title: A Phase I Study to Evaluate the Safety of Trigriluzole (FC-4157/BHV-4157) in Combination with PD-1 Blocking Antibodies

29

RESERVED FOR IRB STAMP  
DO NOT MODIFY THIS SPACE

Form Version v120116

**RUTGERS | eIRB**  
**APPROVED**

IRB ID: Pro20170000453  
Approval Date: 10/4/2019  
Expiration Date: 4/3/2020

Escalation cohort	Trigriluzole dose	Dose Reduction #1	Dose Reduction #2	Dose Reduction #3
Cohort -1	140 mg PO every other day (QOD)	Discontinue Trigriluzole	Discontinue Trigriluzole	Discontinue Trigriluzole
Cohort 1	140 mg PO daily	140 mg PO every other day (QOD)	Discontinue Trigriluzole	Discontinue Trigriluzole
Cohort 2	140 mg PO BID	140 mg PO daily	140 mg PO every other day (QOD)	Discontinue Trigriluzole
Cohort 3	140 mg PO QAM + 280 mg PO QHS	140 mg PO BID	140 mg PO daily	Discontinue Trigriluzole
Cohort 4	280 mg PO BID	140 mg PO QAM + 280 mg PO QHS	140 mg PO BID	Discontinue Trigriluzole

### Pembrolizumab and Nivolumab Dose Modifications

No dose reductions of pembrolizumab or nivolumab are allowed. PD-1 inhibitor must be withheld (not delayed) for drug-related toxicities

Adverse events (both non-serious and serious) associated with PD-1 inhibitor exposure may represent an immunologic etiology. These adverse events may occur shortly after the first dose or several months after the last dose of treatment. For suspected immune-mediated adverse reactions, ensure adequate evaluation to confirm etiology or exclude other causes.

**Grade 3-4 toxicity.** For Grade 3-4 immune-related adverse event (irAE) related to PD-1 inhibitor, withhold PD-1 inhibitor and if indicated, administer corticosteroids as per immune related adverse event guidelines. Upon improvement to Grade 1 or less, initiate corticosteroid taper and continue to taper over at least 4 weeks. Resume PD-1 inhibitor when the adverse reaction remains at Grade 1 or less following corticosteroid taper.

Permanently discontinue PD-1 inhibitor for any Grade 3 immune-mediated adverse reaction that recurs and for any life-threatening immune-mediated adverse reaction. If steroids are indicated longer than 8 weeks, the subject must discontinue treatment with PD-1 inhibitor.

Upon improvement to Grade 1 or less, the subject may resume treatment. The PD-1 inhibitor dose should be skipped (not delayed) and treatment should resume at the next scheduled timepoint.

If the toxicity is liver-related, trigriluzole must also be held (see above). Otherwise, PD-1 inhibitor therapy may be continued at the discretion of the treating investigator.

**Grade 3-4 toxicity.** For Grade 3-4 toxicity that is treatment-emergent and but not an irAE, (examples: fatigue, nausea), PD-1 inhibitor will be held until improvement of toxicity to a Grade 0-1.

**Grade 1-2 Toxicity.** Grade 1-2 adverse events do not require dose adjustment, except if the patient/physician considers them to be serious or intolerable—in this case, the PD-1 inhibitor may be held at the discretion of the treating investigator. An example is grade 2 fatigue.

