### **1.7.7 Dose Modifications and Withholding**

As toxicity of these agents is largely non-overlapping, management of toxicity is dependent on which agent is more likely to have resulted in the toxicity. Vertigo, somnolence, and circumoral paresthesia should be attributed to trigriluzole. Immune-related adverse events should be attributed to the anti- PD-1 antibody. Refer to agent-specific management instructions below for dose modifications and holdings.

*Overlapping toxicities of trigriluzole and anti- PD-1 antibody include fatigue, asthenia, nausea, dizziness, diarrhea, anorexia and liver injury. When these toxicities occur, both drugs should be held until toxicity resolves to grade 0-1.*

Study therapy (both agents) may be held for up to 6 consecutive weeks. Subjects who are not able to resume at least 1 study drug within a period of 6 weeks should be removed from the active treatment phase of the study and begin follow-up procedures.

Dosing interruptions are permitted in the case of medical / surgical events or logistical reasons not related to study therapy (e.g., elective surgery, unrelated medical events, patient vacation, and/or holidays). Missed doses should be omitted, not delayed. Subjects should be placed back on study therapy within 3 weeks of the scheduled interruption, unless otherwise discussed with the study PI or co-PI. The reason for interruption should be documented in the patient's study record. Tumor assessments should continue per the study calendar even if study medication was missed.

Delays due to holidays, weekends and bad weather will be permitted and will not be counted as a protocol violation, and efforts will be made to get the patient back on the original schedule so that assessments are uniform across subjects. If correlative samples are collected and the scheduled treatment that day is delayed/held for any reason, there is no need to re-collect correlative samples.

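### The Grade 3-4 immune-event rule orders the PD-1 inhibitor withheld, then lets it continue whenever the event is not liver-related

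*Combined protocol and SAP*

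**What the plan says.** All the key text is in section 1.7.7 under Pembrolizumab and Nivolumab Dose Modifications.

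- The opening rule is general: "PD-1 inhibitor must be withheld (not delayed) for drug-related toxicities".
- The first Grade 3-4 paragraph is specific: "For Grade 3-4 immune-related adverse event (irAE) related to PD-1 inhibitor, withhold PD-1 inhibitor and if indicated, administer corticosteroids". It has no organ exception.
- Terms for restarting follow. The event must have come down to Grade 1 or less. One statement also requires that it stay there after a steroid taper of at least 4 weeks; another adds: "The PD-1 inhibitor dose should be skipped (not delayed) and treatment should resume at the next scheduled timepoint".
- Permanent stopping is also covered: "Permanently discontinue PD-1 inhibitor for any Grade 3 immune-mediated adverse reaction that recurs and for any life-threatening immune-mediated adverse reaction".
- The block then closes with two sentences. The first reads, up to its closing bracket, "If the toxicity is liver-related, trigriluzole must also be held (see above". The second is "Otherwise, PD-1 inhibitor therapy may be continued at the discretion of the treating investigator".

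The next paragraph deals with Grade 3-4 events that are not immune-related and says the "PD-1 inhibitor will be held until improvement of toxicity to a Grade 0-1".

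**The concern.** *Otherwise* follows directly on the liver condition, so its plain meaning is: when the event does not involve the liver. For those events the closing sentence makes continuing the antibody a matter of discretion, although the same block has already ordered it withheld.

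This is an operative safety instruction in a trial whose primary objective is safety. An investigator who relies on the closing sentence could infuse again during an unresolved severe immune event, and an auditor could not say whether that infusion was a deviation. It also inverts the expected order of caution. Section 1.4.8 names autoimmune effects as the serious risk of these antibodies, yet a severe immune event would get weaker protection than severe non-immune nausea.

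**Working it through.** No formula or planned figure is involved. The check sets the instructions side by side, tests the alternative readings, and then removes the events that other rules already cover.

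**1. Instructions for the PD-1 inhibitor, by type of Grade 3-4 event**

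| Statement in section 1.7.7 | Non-liver irAE | Non-immune event |
|---|---|---|
| Opening rule on drug-related toxicity | Withhold | Withhold, if drug-related |
| Paragraph specific to the event type | Withhold | Hold until Grade 0-1 |
| Closing *Otherwise* sentence | May continue, at discretion | Does not apply |

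For a non-liver irAE, two mandatory statements stand against one permissive sentence. The irAE paragraph alone is enough to create the conflict.

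**2. Alternative readings**

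- *Continued* means resumed after recovery. Restarting already has its own terms in the block, and none of them depends on the liver. This reading does not explain why restarting would turn on liver involvement.
- *Otherwise* means lower grades. Grade 1-2 events have their own paragraph further down, and the sentence sits under a Grade 3-4 heading.
- The wrong drug is named. This fits best: the preceding sentence is about also holding trigriluzole, and section 1.7.7 attributes irAEs to the antibody. It remains an inference about intent, and on this reading the sentence still needs correcting.

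**3. What other rules remove**

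- Recurrent Grade 3 and life-threatening immune reactions: permanent stop of the antibody in the same section. Section 1.7.13 item d also withdraws patients with life-threatening drug-related toxicity from treatment.
- Seven overlapping toxicities named at the start of section 1.7.7 (liver injury, diarrhea, nausea, anorexia, dizziness, fatigue, asthenia): "When these toxicities occur, both drugs should be held until toxicity resolves to grade 0-1". Colitis presenting with diarrhea is therefore already covered.

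What remains is mainly a first-occurrence, non-life-threatening irAE outside that list. Rash is an example: section 1.4.8 counts it among the common reactions to these antibodies, and it is not one of the seven.

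**4. What the two readings mean for one patient treated with steroids**

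Take the restart statement that requires the taper of at least 4 weeks. Doses that come due during a 4-week taper:

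- nivolumab every 2 weeks: 4 / 2 = 2 scheduled doses omitted;
- pembrolizumab every 3 weeks: 4 / 3 = 1.33, so at least 1 scheduled dose omitted.

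Under the *Otherwise* sentence the number that must be omitted is 0. The other restart statement in the block does not mention the taper, so these counts apply only where the taper condition is followed.

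**The case against.** The best case against the concern has four parts.

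- **The opening rule is being over-read.** It may mainly say how to modify treatment (skip, rather than reduce or delay). As an absolute duty it would also clash with the Grade 1-2 paragraph, which requires no adjustment. That is a fair caution about how much weight the rule carries. But the Grade 1-2 paragraph relaxes it only for those grades, and the irAE paragraph is sufficient without it.
- **The block repeats itself.** Restarting is stated twice already, so a third, loosely worded statement about continuing after recovery is possible. This does not explain the link to the liver condition.
- **Outside guidance may settle it.** The irAE paragraph refers to irAE guidelines, sections 1.4.8 and 1.7.4 refer to the prescribing information and package inserts, and section 1.7.13 lets the investigator stop for unacceptable events or a change in condition. The outside sources cannot be seen here and nothing in the protocol says they override the sentence. The section 1.7.13 grounds depend on judgment.
- **The harm is narrow and supervised.** The sentence permits continuation and does not require it, and many oncologists would withhold anyway. Section 4.1.8 makes each infusion conditional on clinician and laboratory assessment. Section 6.3 sends toxicity in the escalation phase to weekly Phase I meetings and dose-limiting toxicities to the oversight committee. These safeguards lower the chance that a wrong infusion goes unnoticed. They do not settle the wording, because the clinician at the pre-infusion assessment applies this same rule.

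The narrowness of the affected group and the existence of oversight both stand. Neither removes the contradiction.

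**Conclusion.** The concern holds: the dosing rule is wrong as written and must be corrected. For a non-liver Grade 3-4 irAE the section says both to withhold the PD-1 inhibitor and that it may be continued, and no visible text resolves this. It is a drafting inconsistency in a safety rule; it does not call the dose-escalation design into question.

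The exposure is limited mainly to first-occurrence, non-life-threatening irAEs outside the seven overlapping toxicities, in any cohort of the 12-27 subjects planned in section 4.1.4. Without an event rate for a single PD-1 antibody in the documents, the number of patients affected cannot be estimated. The dose-limiting toxicity definition in section 6.1 counts related Grade 3 or higher events whether or not the antibody is later withheld, so that count, the escalation rule and the sample size are not directly affected.

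The conclusion rests on the ordinary reading of *Otherwise* as referring to the liver condition. It does not rest on the inference that the wrong drug was named.

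**What to change.** Either of two changes resolves it.

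1. **Delete the closing sentence.** Nothing is lost, because section 1.7.7 already says when trigriluzole is held. This option also avoids assuming what the authors meant.
2. **Replace it**, if the authors confirm that trigriluzole was intended, with: *Otherwise, trigriluzole may be continued if the treating investigator judges it safe, unless the event is one of the overlapping toxicities in section 1.7.7 or is at least possibly related to trigriluzole; in those cases the trigriluzole hold rules above apply.*

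The final condition in the replacement is needed because the Trigriluzole part of section 1.7.7 requires a hold for any Grade 3-4 event even possibly related to that drug. Grade 3 pneumonitis shows why: section 1.4.2 reports interstitial lung disease with riluzole, and it is not among the seven overlapping toxicities.

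Under either option, keep withholding of the PD-1 inhibitor mandatory for every Grade 3-4 irAE. The cost is one sentence deleted or replaced in one section, with no added patients, visits or procedures.

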### **1.7.8 Concomitant Medications**

No investigational or commercial agents or therapies other than those described below may be administered with the intent to treat the patient's malignancy.

**Prohibited Medications.** Systemic steroids (other than those used for replacement of adrenal insufficiency) or treatment of irAE are prohibited. If systemic steroids are indicated longer than 8 weeks, the subject must discontinue study treatment. Prophylactic use of Colony stimulating factors (CSFs) is not permitted. They may be used for supportive care and should be discontinued when the event resolves/improves. If needed longer than 4 weeks, the subject must discontinue study treatment.

The following medicines are inhibitors of CYP1A2 and are prohibited (they may increase blood levels of the active form of the drug, riluzole):

- fluvoxamine
- cimetidine
- amiodarone
- efavirenz
- fluoroquinolones (ciprofloxacin, levofloxacin, moxifloxacin, gatifloxacin, ofloxacin or norfloxacin)
- fluvoxamine
- furafylline
- interferon
- methoxsalen
- mibepradil
- ticlopidine

Subjects who are taking one of these medications at screening will be excluded if it cannot be discontinued. Subjects who are prescribed one of these medications (e.g. fluoroquinolone antibiotic for an infection) while on-study should be switched to another antibiotic as soon as the prescription is noted.

**Strongly Discouraged Concomitant Foods and Medications.** Subjects should be strongly discouraged from using potent CYP1A2 inhibitors and inducers that could affect the metabolism of trigriluzole.

The following medicines are CYP1A2 inducers, which may increase the rate of elimination of the active metabolite riluzole, thus decreasing blood levels. The drugs should be discontinued if possible or another medicine may be substituted in its place:

- Insulin
- Omeprazole
- Carbamazepine
- Modafanil
- Rifampin
- Tobacco and nicotine products

Other common medications given for gastroesophageal reflux disease, such as antacids, esomeprazole, pantoprazole, lansoprazole, famotidine, ranitidine are acceptable to take while on study.

Of note, chronic use of nicotine has modest effects on riluzole exposure (i.e., approximately 30 – 35% reduction in exposure). This effect would not compromise subject safety (as it represents a decrease in exposure). Subjects should be encouraged to consider smoking cessation or reduction, which is the standard of care.

Caffeine is an inhibitor of CYP1A2, however caffeine is considered a prototypical CYP1A2 substrate itself. There is theoretical potential for competitive inhibition; however, caffeine is not typically avoided with other drugs which are reliant on CYP1A2 metabolism. Therefore, subjects may use caffeine without any restriction due to drug interactions.

**Acceptable Concomitant Medications.** All treatments that the investigator considers necessary for a subject's welfare may be administered at the discretion of the investigator

in keeping with the community standards of medical care. Inhaled, topical, and intra-articular steroids are permitted. All concomitant medication will be recorded on the case report form (CRF) including all prescription, over-the-counter (OTC), herbal supplements, and IV medications and fluids. Selected ones include:

- IVIG
- Erythropoietin
- Hormone replacement therapy

**Vaccinations/Immunizations.** Routine vaccinations are prohibited until Week 13, but there are no restrictions on vaccinations after Week 13. If the treating investigator feels that a vaccination is unsafe to delay, an exception may be granted by the PI. It is encouraged to administer the seasonal influenza vaccination (flu shot) prior to study entry.

### **1.7.9 Supportive Care Guidelines**

Patients are allowed to receive full supportive care therapies concomitantly during the study. Supportive medications may be used to treat fever, rash, diarrhea and other common adverse events.

Management of infusion reactions should follow the site's SOPs for infusion or hypersensitivity reactions. Premedications are not required but are allowed for patients with previous infusion reaction.

Radiation therapy may be delivered to a non-target lesion and the patient may remain on-study. For example, radiation therapy may be given to patients with isolated CNS progression.

Surgery or radiation therapy may be performed to palliate a tumor if it is not a target lesion for tumor assessment. If a target lesion requires surgery, the patient should be removed from active treatment due to clinical progressive disease.

### **1.7.10 Adherence/Compliance and Pill Diary**

At each clinic visit each subject will be given a bottle containing capsules of study drug and instructed to return all unused capsules to the investigator. Patients will be given a Pill Diary and instructed to record the number of capsules taken and the time taken.

There are 3 different pill diaries for different portions of the protocol:

#### **1. Trigriluzole Lead-in Period**

Protocol Number: RCINJ# 051707

PI Name: [name]

Protocol Title: A Phase I Study to Evaluate the Safety of Trigriluzole (FC-4157/BHV-4157) in Combination with PD-1 Blocking Antibodies

33

RESERVED FOR IRB STAMP  
DO NOT MODIFY THIS SPACE

Form Version v120116

**RUTGERS | eIRB**  
**APPROVED**

IRB ID: Pro20170000453  
Approval Date: 10/4/2019  
Expiration Date: 4/3/2020

2. Trigriluzole + Nivolumab
3. Trigriluzole + Pembrolizumab

Study staff should select the appropriate Pill Diary to give to the subject. Subjects will be strongly encouraged (but not required) to keep a pill diary to assess adherence as accurately as possible.

At the end of each cycle of treatment, the actual amount of unused drug will be compared to the amount taken as recorded on the subject's medication diary/verbal report. The desired level of compliance is  $\geq 75\%$ . Patients who cannot maintain this level of compliance may be removed from the study. If a subject is not compliant, the treating investigator should reeducate the subject, assess barriers to compliance, and address correctable barriers.

#### **1.7.11 TOXICITY MONITORING AND ADVERSE EVENT REPORTING**

All patients who receive one dose of protocol therapy will be evaluable for assessment of toxicity. Prior to each cycle the treating physician will fully assess the patient's condition with respect to possible treatment related toxicities. All adverse events, whether observed by the physician or reported by the patient, occurring during the active portion of therapy, or up to 30 days after the last dose of treatment will be graded by a numerical score according to the NCI's Common Terminology Criteria for Adverse Events (CTCAE), Version 4.0

(<http://ctep.cancer.gov/reporting/ctc.html>) and recorded in the patient's medical record. For the purposes of reporting laboratory abnormalities, only Grade 3-4 adverse events will be recorded on the adverse event CRF pages. Grade 1-2 laboratory abnormalities will not be recorded on the adverse event CRF pages, unless the investigator judges it to be clinically significant and wishes to report it. Information entered on the adverse event CRF pages will include:

- Specific type and duration of reaction (i.e., start and stop dates, resolution).
- Severity/grade.
- Relationship to study drug (causality, attribution).
- Management of the event, if treated with medication and other actions taken to alleviate the clinical event.
- Whether or not it was considered a SAE.

A preexisting condition is one that is present at the start of the study. A preexisting condition will be recorded as an adverse event if the frequency, intensity, or the character of the condition worsens during the study period.

### **Adverse Event Reporting Requirements**

An adverse experience is defined as any unintended or abnormal clinical observation that is not of benefit to the patient. Either the condition was not present prior to exposure to the study therapy, or it has worsened in intensity or frequency following exposure to the study therapy.

### **SAE Reporting Period**

The SAE reporting period starts at start of treatment and lasts through 30 days after the patient's last dose or start of subsequent therapy, whichever comes sooner. SAE's that during screening period prior to the start of therapy are presumed to be unrelated to the study and need not be reported as SAEs.

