### **SAE Reporting Timeline**

All "unexpected" (defined below) and/or "serious" (defined below) adverse events related to pembrolizumab/nivolumab or the combination of pembrolizumab/nivolumab + trigriluzole and occurring during the active portion of therapy, or up to 30 days after the last dose of treatment, will be reported to the Office of Human Research Services at [contact] or [contact]. Events will be promptly reported, in writing, to the local IRB in accordance with IRB policy. If a death occurs the IRB will be notified **within 24-hours** of initial receipt of information. All other SAEs must be reported to the IRB **within 3 to 10 days** of initial receipt of information. Written follow-up reports are required when additional information is needed to fully characterize the event. Copies of each report sent to the IRB will be kept in the study regulatory file.

Collaborating institutions will report all SAEs to RCINJ Office of Human Research Services (OHRs) and RCINJ OHRs will be responsible for forwarding SAE reports to the IRB, FDA, Fox Chase Chemical Diversity Center, Inc. and Biohaven Pharmaceuticals.

In addition to reporting to the local IRB, reporting to external bodies such as industry and/or the FDA may be necessary.

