 **RUTGERS | eIRB**  
APPROVED  
Form Version v120116

IRB ID: Pro20170000453  
Approval Date: 10/4/2019  
Expiration Date: 4/3/2020

	Off treatment but on study Q6 weeks	Off treatment but on study Q12 weeks	Safety Follow-up (12 weeks after last dose of rx)	Long-Term Follow-up Q12 weeks
Scheduling Window (Days):	±14	±14	±28	± 28
Prior and Concomitant Medication Review	X	X	X	
Assess Baseline Symptoms/Adverse Events and Compliance	X	X	X	
Vital Signs and Weight, ECOG Performance Status, Physical Examination	X	X	X	
Routine Safety Laboratory Studies	X	X	X	
Tumor Assessment 		X	X	
Post-study survival status, and receipt of subsequent anticancer therapy				X

Footnotes

1. If a subject has discontinued active treatment due to reasons other than PD (such as toxicity or patient preference), the subject will continue to have CT scans and follow-up visits to monitor them until Week 49.
2. Tumor Assessment must be performed at the same Weeks as subjects who remain on active treatment (Week 7, Week 13, and then Q12 weeks up until Week 49).
3. Safety follow-up visit will occur at Week 61 for subjects who complete all treatment (Week 49), but it will occur prior to Week 61 if active treatment is discontinued early for PD or other reasons.
4. Long-term Follow-up. Subjects will remain in the follow up phase of the trial for up to 3 years until the start of another therapy, withdrawal of consent or death.

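### The defined windows for AE recording and SAE reporting close 30 days after last dose, so later immune events found at the scheduled 12-week safety visit have no stated grading, CRF or reporting rule

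*Combined protocol and SAP*

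**What the plan says.** Three paragraphs of Section 1.7.11 set the capture windows.

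- The opening paragraph covers adverse events "occurring during the active portion of therapy, or up to 30 days after the last dose of treatment will be graded by a numerical score" and then recorded.
- The SAE Reporting Period starts with treatment and runs to 30 days after the subject's "last dose or start of subsequent therapy, whichever comes sooner".
- The SAE Reporting Timeline covers related events that are serious or unexpected, on therapy "or up to 30 days after the last dose of treatment, will be reported to the Office of Human Research Services". It does not mention subsequent therapy.

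Other sections look further ahead. Section 1.7.7, under Pembrolizumab and Nivolumab Dose Modifications, says of PD-1 inhibitor events that may be immunologic: "These adverse events may occur shortly after the first dose or several months after the last dose of treatment". The follow-up calendar in Section 1.10 has a column headed "Safety Follow-up (12 weeks after last dose of rx", with a window of ±28 days and with AE assessment, physical examination and safety laboratory tests marked. Its footnote 3 brings in subjects who stop early: "it will occur prior to Week 61 if active treatment is discontinued early for PD or other reasons". Section 1.3.6 adds 12-weekly toxicity assessments, or AE contact for those who cannot attend, for subjects who stop for reasons other than progression, up to one year from the start of treatment.

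**The concern.** The protocol describes a delayed risk and schedules a visit at which it could be seen, but the rules for writing that risk down end before the visit takes place. Staff who find a new immune event at the 12-week visit are told to assess it. They are not told whether to grade it, enter it on the AE form or report it as an SAE, and different staff may decide differently.

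The kind, grade and frequency of adverse events is a secondary endpoint (Section 1.1.3), and Section 6.1 plans to tabulate AE and SAE frequencies. If late events enter that table only by individual judgement, the frequencies have no fixed observation period. The SAE rule adds a second difficulty: two adjacent paragraphs give different end dates for a subject who starts another therapy within 30 days.

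**Working it through.** The plan gives no figure to reproduce. The check is date arithmetic and a comparison of the texts.

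**Inputs**
- Recording and reporting window: 30 days after last dose (Section 1.7.11).
- Safety visit: 12 weeks after last dose, ±28 days (Section 1.10, follow-up calendar).

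**Timing**
- Scheduled visit: 12 × 7 = day 84. Footnote 3 agrees for subjects finishing at Week 49: 61 − 49 = 12 weeks.
- Permitted range: 84 − 28 = day 56 to 84 + 28 = day 112.
- Gap between the close of the window and the visit: 84 − 30 = 54 days (56 − 30 = 26 to 112 − 30 = 82).
- Share of the interval covered: 30/84 = 36% (30/112 = 27% to 30/56 = 54%).

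Even the earliest permitted visit falls after the window has closed. An event that began by day 30 and is still present at the visit is inside the rules; the gap concerns events that begin after day 30.

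**What applies to an event that begins after day 30**

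| Step | Text | Covered? |
|---|---|---|
| Assessment | 1.3.6; 1.10 follow-up calendar | Yes |
| Data collection in general | 6.3, Frequency of Data Collection: at each visit and follow-up contact, no end date | Implied, no detail |
| Grading and AE form | 1.7.11, opening paragraph | No |
| SAE reporting to the research office and IRB | 1.7.11, SAE Reporting Period and Timeline | No |
| FDA report | 1.7.11, paragraphs on commercial drugs and on trigriluzole | Only if serious, unexpected and related |
| Long-term follow-up | 1.3.7: survival and subsequent therapy only | No |

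The FDA route is narrow. Section 1.7.11 defines an event as unexpected when it is absent from the brochure or package insert, so an immune event already listed there does not qualify.

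**The conflict over subsequent therapy**

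Suppose a new therapy starts before day 30. From that date to day 30, the Reporting Period is closed while the Reporting Timeline is still open for related events. One could read the Reporting Period as 30 days after whichever event comes first. Since subsequent therapy follows the last dose, the clause would then never shorten anything. Only the reading that ends SAE reporting at the new therapy gives it any effect.

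**Scale**

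With the planned 12 to 27 subjects (Section 6.1), one subject with an unrecorded late event changes a reported proportion by 1/27 = 3.7 to 1/12 = 8.3 percentage points. This shows sensitivity; it does not predict that such an event will occur.

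**The case against.** The best reply is that later events are still looked for. The follow-up calendar marks AE assessment in every off-treatment column and at the safety visit, Section 1.3.6 requires 12-weekly checks or contacts, and Section 6.3 gives safety data collection a start and no end. A reader might infer from the 30-day limit that delayed events go unseen or are lost. The documents do not support that. What is missing is a rule for what happens to such an event once it has been found.

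Three further points stand.

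- **FDA reporting.** Serious, unexpected, related events must go to the FDA with no 30-day limit and no cut at new therapy, so late events are not wholly outside the reporting rules.
- **Subsequent therapy.** A reader might conclude that all safety capture ends when a new therapy starts. Only the SAE Reporting Period says so; AE recording and the SAE Reporting Timeline both run to day 30 regardless. The defect is the disagreement between the paragraphs.
- **Size.** The 36% counts days. The documents give no distribution of onset times after last dose, so the remaining 64% cannot be read as a proportion of events missed.

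It is also fair to say that 12 weeks is partly a matter of choice. Section 1.7.7 speaks of months, and some events could begin after day 84. The argument for 12 weeks is that the visit already exists.

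These points narrow the concern. They do not remove it, because Section 6.3 supplies no grading or reporting rule, and Section 6.1 needs a defined period over which to count events.

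**Conclusion.** The point holds as a conflict between the capture windows and the follow-up schedule. The windows close 54 days before the scheduled safety visit (26 to 82 days) and cover 36% of the follow-up time to it (27% to 54%). Events that begin after day 30 are assessed but, outside the FDA route, have no grading, CRF or SAE rule. The two SAE paragraphs also disagree about subsequent therapy.

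The likely effect is some under-counting of late immune events in a secondary endpoint that is analysed descriptively. How much cannot be estimated from the documents. A reader might go further and doubt the dose finding. That does not follow: DLTs are counted in the first weeks of treatment (Section 6.1), so the escalation decisions and the MTD/RP2D do not depend on this window.

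The conclusion assumes that Section 1.7.11 is followed as written and that no separate data-capture instruction extends it. Section 6.2 mentions a study-specific data capture plan, which is not among the documents. The change is worth making because it is cheap.

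**What to change.** 1. In Section 1.7.11 (opening paragraph, SAE Reporting Period and SAE Reporting Timeline), extend grading, CRF recording and SAE reporting of treatment-related and immune-related events to the existing 12-week safety visit.
2. Make the two SAE paragraphs agree by not ending capture of related events at the start of subsequent therapy.
3. Align the rest. Section 6.3 should give the same end date. Section 1.3.6 should say how events found at the 12-weekly contacts are recorded. Section 1.3.7 and the calendar footnotes should say how the safety visit applies to a subject who has started another therapy, since the follow-up phase is now worded to end there. Footnote 3 should also be reconciled with the 109-week maximum in Section 1.3.2, because it describes completion at Week 49.

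This adds 54 days of defined capture per subject (26 to 82 with the visit window). Sample size, DLT rules and the MTD procedure do not change, and no new visit type is needed. The cost is amendment wording and a few more AE and SAE forms. Events that begin after a new therapy has started will be harder to attribute, so the date of that therapy should be recorded with them.
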